# Effects of Romosozumab on Bone Mineral Density, Markers of Bone Metabolism and Bone Microarchitecture in Women with Anorexia Nervosa: A Pilot Study

## I. Background/Significance

Anorexia nervosa is a serious disease leading to severe bone loss at multiple skeletal sites. The illness affects 1-2% of young women in the U.S. and is chronic in more than 50% of affected women. Bone loss is a severe, frequent and often permanent comorbid medical complication resulting in debilitating vertebral crush fractures. The majority of women with anorexia nervosa have bone loss, and 50% have bone density measurements greater than 2 standard deviations below normative means. It is not uncommon for bone mass in these young women to be comparable to postmenopausal women in their 7th and 8th decades. Undernutrition, loss of muscle mass (which is an unavoidable consequence of weight loss), and endocrine hormone dysregulation [particularly low insulin-like growth factor 1 (IGF-1)] all contribute to low bone mass in women with anorexia nervosa.

Although bone density increases with weight recovery, osteopenia is often a permanent consequence of anorexia nervosa. Significant persistent osteopenia in women with anorexia nervosa has been shown in many studies and both cortical and trabecular bone mineral density (BMD) remain low more than ten years after recovery. Because bone mass remains persistently low despite recovery, such women remain at a high fracture risk throughout life, estimated to be 7.1 times that of healthy women in this age range. These data suggest that there may be a therapeutic window during which effective treatment should be implemented to prevent significant, lifelong bone mass reduction in this vulnerable population.

Adulthood in anorexia nervosa is characterized by a negative balance in bone metabolism, with decreased bone formation and increased bone resorption (Figure 1), including lower levels of osteocalcin, a marker of bone formation, and higher levels of deoxypyridinoline (DPYRX) and N-telopeptide (NTX), markers of bone resorption, than age- and sex-matched controls (Figure 1).

[figure not shown]

Figure 1. Levels of osteocalcin (a), a marker of bone formation, are decreased in women with anorexia nervosa compared to controls. Levels of deoxypyridinoline (DPYRX) (b) and N-telopeptide (NTX) (c), markers of bone resorption, are increased in women with anorexia nervosa compared to controls.

A number of therapies targeting the high resorptive state in women with anorexia nervosa have been studied in women with anorexia nervosa, primarily by our group. We have shown that neither low-dose estrogen at postmenopausal hormone replacement doses or oral contraceptives are effective in women with anorexia nervosa, and bisphosphonates increase bone density significantly but not to normal.

Agents that are anabolic to bone have been examined in pilot studies by themselves or in combination with anti-resorptives. The most promising of such agents in terms of effectiveness may be parathyroid hormone, but it is not approved by the FDA for young women due to concerns about a possible risk of osteosarcoma. We have also studied low-dose recombinant insulin-like growth factor 1 (IGF-1), which is anabolic to bone and demonstrated modest increases in bone density that did not come close to normalizing bone density in women with anorexia nervosa, and low-dose testosterone, which was ineffective. This suggests that both high bone resorption and low bone formation characteristic of women with anorexia nervosa are logical and critical therapeutic targets, but that a more potent medication such as romosozumab that addresses both the deficit in bone formation and increased bone resorption is needed. In addition, as anorexia nervosa is a psychologic illness and such patients are often overwhelmed by the requirements of therapy and the illness itself, a treatment such as romosozumab administered monthly by a healthcare clinician may have the benefit of increased compliance and therefore efficacy, as we have observed in our ongoing pilot study in which the lower frequency of Prolia administration has resulted in the lowest drop-out rate of any study in anorexia nervosa yet in our hands – and likely in anyone’s. In addition, we have experienced outstanding excellent compliance to calcium and vitamin D supplementation in our ongoing pilot study of Prolia vs placebo, with no hypocalcemia. Exceptional compliance with supplementation in women with anorexia nervosa has also been reported in other studies.

There are no therapies that normalize BMD or that are FDA-approved for bone loss in anorexia nervosa, and in contrast to postmenopausal osteoporosis in which therapy may be life-long, the goal in patients with anorexia nervosa is treatment during the acute illness to reduce further bone loss and fracture risk. We propose that an early relatively short-term intervention with a potent combination anabolic and anti-resorptive therapy such as romosozumab during the period of rapid bone loss is an ideal, targeted therapy for the unique dysregulation of bone metabolism of young women with anorexia nervosa and may prevent significant osteopenia and reduce fracture risk in women with anorexia nervosa. We propose romosozumab therapy in a young, low-weight, population of women in which the prevalence of cardiovascular disease is extremely low. Therefore, even if the possible signal implicating romosozumab in cardiovascular risk proves to have validity, this group of women would be at particularly low risk for such a complication.

## II. Specific Aims

### Phase 1: Romosozumab vs placebo

This █-sponsored investigator-initiated protocol is a randomized, double-blind, placebo-controlled clinical trial which aims to investigate the effect of romosozumab on BMD in women with anorexia nervosa. We will also investigate the safety of romosozumab in women with anorexia nervosa. We hypothesize that 12 months of romosozumab administration will result in an increase in bone mineral density, increase in markers of bone formation and decrease in markers of bone resorption, and improvement in bone microarchitecture in osteopenic women with anorexia nervosa compared with placebo.

**Specific Aim 1:** We hypothesize that 12 months of romosozumab administration will result in an increase in bone mineral density in women with anorexia nervosa with low bone mass or osteoporosis compared with placebo.

We will investigate in women with anorexia nervosa in a 12-month study whether treatment with romosozumab will increase BMD as measured by dual energy x-ray absorptiometry (DXA) compared with placebo. The primary endpoint will be change in lumbar spine BMD from baseline to 12 months. Bone density will be measured at baseline, 6 months and 12 months.

**Specific Aim 2:** We hypothesize that 12 months of romosozumab administration will result in a significant increase in markers of bone formation and reduction of markers of bone resorption in osteopenic women with anorexia nervosa compared with placebo.

We will investigate in women with anorexia nervosa in a 12-month study whether markers of bone formation, including osteocalcin and P1NP, will increase in the romosozumab group more than in the placebo group. We will also investigate whether markers of bone resorption, including CTx, will decrease in the romosozumab group more than in the placebo group. Markers of bone metabolism will be measured at baseline, 3 months, 6 months, 9 months and 12 months.

**Specific Aim 3:** In this exploratory aim, we hypothesize that 12 months of romosozumab administration will result in improved bone microarchitecture and strength in osteopenic women with anorexia nervosa compared with placebo.

We will investigate in women with anorexia nervosa in a 12-month study whether treatment with romosozumab will improve bone microarchitecture, as assessed by HR-pQCT, and improve bone strength, as estimated by microfinite element analysis compared with placebo. HR-pQCT of the tibia and radius will be performed and the following will be measured: trabecular thickness and spacing; cortical thickness and porosity; ITS (individual trabecula segmentation); finite element analysis modeling of bone strength. HR-pQCT will be measured at baseline, 6 months and 12 months.

**Specific Aim 4:** In this exploratory aim, we hypothesize that increases in bone mineral density will be greater in women with anorexia nervosa randomized to romosozumab who gain lean mass over 12 months compared to women randomized to romosozumab who do not gain lean mass over 12 months, and lowest in women randomized to placebo.

We will investigate in women with anorexia nervosa in a 12-month study whether increases in lean mass over 12 months are associated with a greater effect of romosozumab in increasing bone mineral density. It is known that muscle has an anabolic effect on bone through mechanical loading and muscle-bone hormonal cross-talk. Low lean body mass has been associated with impaired bone mineral density, bone microarchitecture, and estimated bone strength in women with anorexia nervosa . Although studies have demonstrated that women continue to have reduced bone mineral density years after the onset of recovery from anorexia nervosa , we hypothesize that the beneficial effects of romosozumab will be greater in women who gain lean mass during the 12 months of the study. We are exploring an association between lean body mass gain and BMD gain, and not causality. Lean mass and LS BMD will be measured by DXA at 0 and 12 months.

## Phase 2: Zoledronic acid

### **Specific Aims:**

In Phase 2, participants will receive a single infusion of open-label zoledronic acid (an intravenous bisphosphonate) 5 mg after the initial 12-month administration of romosozumab or placebo. We hypothesize that 12 months of romosozumab followed by a single intravenous infusion of open-label zoledronic acid will result in a greater increase in BMD compared to 12 months of placebo followed by a single intravenous infusion of open-label zoledronic acid. Within the group of women who receive sequential therapy with 12 months of romosozumab followed by a single intravenous infusion of zoledronic acid, we hypothesize that BMD will be maintained between 12 and 24 months following administration of zoledronic acid.

**Specific Aim 1:** We hypothesize that 12 months of romosozumab followed by a single intravenous infusion of open-label zoledronic acid will result in a greater increase in BMD compared to 12 months of placebo followed by a single intravenous infusion of open-label zoledronic acid.

We will investigate whether sequential therapy of 12 months of romosozumab followed by a single intravenous infusion of open-label zoledronic acid results in a significantly greater increase in BMD from baseline to 24 months compared to 12 months of placebo followed by a single intravenous infusion of open-label zoledronic acid. The primary endpoint will be lumbar spine BMD at 24 months in the romosozumab/zoledronic acid group compared to the placebo/zoledronic acid group. BMD will be measured at baseline and 24 months.

**Specific Aim 2:** We hypothesize that within the group of women who receive sequential therapy with 12 months of romosozumab followed by a single intravenous infusion of open-label zoledronic acid, BMD will be maintained between 12 and 24 months following administration of zoledronic acid.

We will investigate whether a single intravenous infusion of open-label treatment with zoledronic acid will maintain the hypothesized gains in BMD achieved after 12 months of romosozumab administration. The primary endpoint will be lumbar spine BMD at 24 months. BMD will be measured at 12 and 24 months.

### **III. Subject Selection**

Approximately 75 women will be screened for eligibility in order to identify 30 eligible women with anorexia nervosa, ages 20 to 60, to enroll in the study. Subjects will be randomized in a double-blind fashion to one of two groups for 12 months: monthly 1) romosozumab (210 mg, which must be administered as two injections of 105 mg) or 2) two identical placebo injections to determine effects on BMD, markers of bone metabolism, bone microarchitecture, and bone strength at trabecular and cortical sites. All subjects will meet the DSM-V criteria for AN or atypical anorexia and will be assessed for study suitability and monitored throughout the study period for their overall psychiatric clinical state in coordination with the patients' clinical care team by a study psychologist or psychiatric nurse practitioner.

### **Inclusion/Exclusion Criteria:**

#### **Inclusion Criteria:**

- Female

- Age 20-60 years, skeletally mature with closed epiphyses
- Body mass index (BMI)  $\geq 16.5 \text{ kg/m}^2$
- Anorexia nervosa or atypical anorexia nervosa defined by DSM-V diagnostic criteria
- BMD Z-score  $< -1.0$
- Normal serum 25-OH vitamin D ( $>30 \text{ ng/mL}$ ) and calcium levels
- For women of reproductive age, agree to use an effective contraceptive method. Highly effective methods of birth control include:
  - Combined (estrogen and progestogen) hormonal methods (pills, vaginal ring, or skin patch)
  - Intrauterine device (IUD)
  - Intrauterine hormonal-releasing system (IUS)
  - Surgery to tie both fallopian tubes (bilateral tubal ligation/occlusion)
  - Woman's male partner has had a vasectomy and testing shows there is no sperm in the semen
- Dental check-up within the past year

**Exclusion Criteria:**

- Hospitalization within 3 months of baseline study visit, including inpatient eating disorder treatment facility; participating in a residential eating disorder treatment program within 3 months of study participation is permitted
- Myocardial infarction or stroke within 1 year preceding enrollment
- History of hypertension or use of anti-hypertensive medications within the past 6 months
- Any disease known to affect bone, including untreated thyroid dysfunction, Cushing's or renal failure
- Any medication known to affect bone metabolism within 3 months of the study, excluding oral contraceptives or other forms of estrogen administration. Bisphosphonates must have been discontinued for at least one year before participation
- Immunodeficiency or taking immunosuppressive therapy
- Serum 25-OH vitamin D level  $<30 \text{ ng/mL}$
- Serum potassium  $<3.0 \text{ meq/L}$
- Serum magnesium  $<1.5 \text{ meq/L}$
- Serum ALT  $>3$  times upper limit of normal
- eGFR of less than 30 ml/min
- LDL  $> 190 \text{ mg/dL}$
- Hypocalcemia
- Diabetes mellitus
- Active substance abuse, including alcohol
- Current smoker
- History of malignancy
- Paget disease of bone
- Osteomalacia

- Osteonecrosis of the jaw (ONJ) or risk factor for ONJ, such as invasive dental procedures (eg, tooth extraction, dental implants, oral surgery in the past 6 months), poor oral hygiene, periodontal and/or pre-existing dental disease, and current use of corticosteroids.
- Planned invasive dental procedure over the next 24 months
- Known sensitivity to any of the products or components of the medication to be administered
- Sensitivity to calcium or vitamin D supplements
- Pregnant, planning to become pregnant within 12 months after the end of treatment and/or breastfeeding
- Subjects with a known esophageal disease
- Abnormalities of the esophagus such as stricture or achalasia
- Inability to sit/stand upright for at least 30 minutes
- Hypersensitivity to any component of zoledronic acid

**Drop Criteria (conditions for withdrawing subjects). These criteria (other than pregnancy) apply until the zoledronic acid infusion has occurred:**

- Pregnancy (for any subject)
- BMI < 16.0 kg/m^2 at two consecutive study visits at which weight and height are measured
- Hospitalization, including inpatient eating disorder treatment facility; participation in a residential eating disorder treatment program is permitted
- Medical instability, which will be determined by the study physician. Patients in this category will be assessed by the Data Safety Monitoring Board and continue to be assessed according to study protocol.
- Serious study-related adverse event

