injections may be mailed to and administered by an out-of-state, licensed physician, physician assistant, or nurse practitioner responsible for the clinical care of the study subject. A urine pregnancy test (unless exempt from urine hCG) and clinical evaluation will be performed at each monthly visit. A bionutrition evaluation, including weight in a gown, height, and calculation of percent IBW and body mass index (BMI), will be performed at months 3, 6, 9, and 12. At months 1, 3, 6, 9, and 12, blood testing, including for electrolytes (e.g. calcium), will occur unless performed clinically within 2 weeks prior to the study visit. Calcium and eGFR must be normal and 25-OH vitamin D must be  $> 20$  ng/mL at the most recent visit in order to receive zoledronic acid at the 12-month visit. If labs are not normal, study staff will reach out to the participant's care team to assist with timely intervention with the goal that repeat labs are normal prior to the 12-month visit. Participants with serum 25-OH vitamin D  $\leq 20$  ng/ml at the 9-month visit will be given oral vitamin D2 (ergocalciferol) 50,000 IU weekly, and their 25-OH vitamin D level will be rechecked at the 11-month visit. If their repeat serum 25-OH vitamin D level at the 11-month visit is still  $\leq 20$  ng/ml, we will continue to provide oral vitamin D2 (ergocalciferol) 50,000 IU weekly, and their 25-OH vitamin D level will be rechecked every 2 weeks until their 25-OH vitamin D level meets the requirement ( $> 20$  ng/ml) to receive zoledronic acid. Additionally, participants will be given one loading dose of oral vitamin D2 (ergocalciferol) 50,000 IU at the 12-month visit if their most recent 25-OH vitamin D level is  $< 30$  ng/ml. At months 3, 6, 9 and 12, questionnaires will be completed (EDI-3 and EDE-Q). Additionally, at months 6 and 12, a Paffenbarger exercise questionnaire will be completed. A calcium and vitamin D food frequency questionnaire will be completed at the month 12 visit as well. DXA at the spine, hip, radius and total body for BMD and body composition, including lean mass, will be performed 6 and 12 months after baseline. HR-pQCT and FEA of the radius and tibia will be performed at 6 and 12 months. Markers of bone metabolism will be measured at months 3, 6, 9 and 12.

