A clinical evaluation and pregnancy test (unless exempt from urine hCG) will be performed at the 18 and 24-month visits, as will a nutrition evaluation, including weight in a gown, height, and calculation of percent IBW and body mass index (BMI) and completion of questionnaires (EDI-3, EDE-Q, and Paffenbarger exercise questionnaire). A calcium and vitamin D food frequency questionnaire will also be administered at the month 24 visit. At 18 and 24 months, markers of bone metabolism will be measured, and safety labs will be performed, unless performed clinically within 2 weeks prior to the study visit. DXA at the spine, hip, radius and total body will be performed at the 24-month study visit. HR-pQCT and FEA of the radius and tibia will also be performed at 24 months.

For the 18-month visit, subjects who do not live locally will be permitted to have their blood drawn and pregnancy test performed offsite for lab tests required for the visit. Tests that need to be run in real time will be done at local laboratories, with the results provided online to investigators. Otherwise, the samples will be mailed to investigators. Subjects who choose this option will also have an interim history performed by our staff by telephone.

Additionally, for all visits which involve questionnaires, those will be completed on paper during the visit or sent electronically via Redcap to be completed and returned to study staff.

Study Visit	Screen	Baseline	M1	M2	M3	M4	M5	M6	M7	M8	M9	M10	M11	M12	M18	M24
Consent	X															
Clinical assessment	X	X			X			X			X			X	X	X
HCG	X	X	X	X	X	X	X	X	X	X	X	X	X	X	X	X
Safety Labs (CBC, magnesium, and CMP at screen; BMP, calcium, magnesium, and albumin thereafter)	X	X	X		X			X			X			X	X	X
Study drug (romosozumab) or placebo injection			X	X	X	X	X	X	X	X	X	X	X			
Zoledronic acid infusion														X		
Nutrition Evaluation (height, weight)	X	X			X			X			X			X	X	X
Bone Markers (CTX, P1NP, osteocalcin)			X		X			X						X	X	X
IGF-1			X					X						X		
25-OH VitD	X										X					
Direct LDL	X															
Electrocardiogram (ECG or EKG)	X															
BMD (DXA)	X	X						X						X		X
Bone Strength with FEA (Xtreme CT)		X						X						X		X
EDI-3			X		X			X			X			X	X	X
EDE-Q			X		X			X			X			X	X	X
Paffenbarger Questionnaire (exercise quantification)			X					X						X	X	X
Calcium and Vitamin D Food Frequency Questionnaire			X											X		X

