### **Data Analysis Plan:**

The data analysis plan for the study will be as follows. The primary analysis will be intention-to-treat, with the primary endpoint being change in PA lumbar spine aBMD. Statistical significance will be defined as a two-tailed p-value of  $\leq 0.05$ .

Phase 1 Aims 1-3: Baseline mean clinical characteristics between the 2 groups will be compared by t-test. Variables will be tested for normality using the Shapiro-Wilk test, and if non-normal, variables will be log-transformed before analysis. If the distribution remains non-normal after log-transformation, nonparametric testing using the Wilcoxon rank sum test will be performed instead. The analysis of variables at 12 months will be performed using a linear random effects model to estimate and test the effects of the 2 randomization groups (romosozumab vs placebo) from baseline to 12 months on the study endpoints.

Phase 1 Aim 4: The analysis of variables at 12 months will be performed using a linear random effects model to estimate and test the effects of the 2 randomization groups (romosozumab vs placebo) from baseline to 12 months on the study endpoints. We will also add a lean body mass x randomization group interaction term to examine if the effects of body mass change differ between romosozumab and placebo.

Phase 2 Aim 1: The analysis of variables at 24 months will be performed using a linear random effects model to estimate and test the effects of the 2 randomization groups (12 months of romosozumab followed by a single intravenous infusion of open-label zoledronic acid vs 12 months of placebo followed by a single intravenous infusion of open-label zoledronic acid) from baseline to 24 months on the study endpoints.

Phase 2 Aim 2: A secondary analysis will be performed to determine whether gains achieved in the romosozumab group are maintained through the subsequent 12-month study period using a linear random effects model with the fixed effect being time and the random effect being the intercept. Lack of statistical significance will indicate maintenance (lack of decrease--or increase) of BMD.

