**Atypical femoral fractures.** An atypical femoral fracture is an unusual thigh bone fracture that may occur with little or no trauma. Fractures can occur in both thighs at the same time. Atypical fractures have been reported rarely in patients receiving romosozumab. It is unknown whether the risk of atypical femoral fracture continues after stopping therapy. It can present with new or unusual hip, thigh, or groin pain weeks to months before the fracture is diagnosed. Subjects will be instructed that if they develop any of these symptoms, they should report them to the study doctor and the physician they see for clinical care. Patients presenting with an atypical femur fracture will also be assessed for symptoms and signs of fracture in the contralateral limb.

In clinical studies, after romosozumab discontinuation, BMD returns to approximately baseline levels within 12 months in the absence of follow-up antiresorptive therapy. This is why we propose to follow the 12 months of romosozumab or placebo with a single intravenous infusion of open-label zoledronic acid at the 12-month visit.

The potential effects of romosozumab on the fetus are not known, and therefore precautions against administration to pregnant patients will be instituted. All patients will have pregnancy tests on admission prior to receiving study medication and serial pregnancy tests at every study visit and will be required to use contraception in order to participate in the protocol (unless exempt). Any subject who becomes pregnant during the course of the study and is discharged from participation, will undergo a follow-up study visit. This will include assessment by an MD or NP for study medication related side effects, including hypocalcemia, and measurement of a calcium level if it has not been done clinically.

After patients start taking romosozumab, it is possible that their body may make antibodies to romosozumab. Antibodies to romosozumab have not been associated with changes in the efficacy or safety of romosozumab.

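### Three of the four non-pregnancy drop criteria have no stated DXA follow-up, so illness-related month-12 and month-24 BMD may go uncollected

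*Combined protocol and SAP*

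**What the plan says.** Section III of the protocol gives the withdrawal conditions under the heading "Drop Criteria (conditions for withdrawing subjects). These criteria (other than pregnancy) apply until the zoledronic acid infusion has occurred". The infusion is due at month 12, so the four non-pregnancy criteria apply throughout the primary-endpoint period. Follow-up after a criterion is met differs by criterion:

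- **Medical instability** (a clinical judgement): "Patients in this category will be assessed by the Data Safety Monitoring Board and continue to be assessed according to study protocol".
- **Pregnancy** (section VII, Romosozumab Administration): one follow-up visit for side effects and calcium, with no DXA mentioned.
- **Low BMI, hospitalisation, serious study-related adverse event**: nothing is stated.

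Section V describes no early-termination DXA, and no section separates stopping study drug from leaving the study. The scheduled scans are at baseline, then Phase 1 DXA "including lean mass, will be performed 6 and 12 months after baseline", and finally "DXA at the spine, hip, radius and total body will be performed at the 24-month study visit". For weight, "calculation of percent IBW and body mass index (BMI), will be performed at months 3, 6, 9, and 12".

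The Data Analysis Plan in section VI states: "The primary analysis will be intention-to-treat, with the primary endpoint being change in PA lumbar spine aBMD". It names a linear random effects model and gives no missing-data assumption or sensitivity analysis. Section V replaces only women who withdraw before completing the baseline visit. For Phase 2 Aim 1, "The primary endpoint will be lumbar spine BMD at 24 months in the romosozumab/zoledronic acid group compared to the placebo/zoledronic acid group".

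**The concern.** An intention-to-treat analysis is only as complete as the outcomes collected. Because continued assessment is spelled out for one criterion, site staff may reasonably read withdrawal under the other three as the end of scanning.

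Two of those three triggers, low weight and hospitalisation (including inpatient eating-disorder care), are tied to the illness. Section I itself names undernutrition and loss of muscle mass as contributors to low bone mass. A missing month-12 BMD may therefore carry information about the value that was not measured. With 10 women on placebo, each lost scan is 10% of that arm.

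The rule also treats similar women differently by timing. A woman hospitalised after the infusion keeps her month-24 DXA. For one hospitalised at month 9, no later scan is stated.

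**Working it through.** **1. The plan's own figure.** Inputs from section VI: 20 versus 10 women, difference 9 percentage points, SD 8, two-sided alpha 0.05, equal-variance t-test.

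Standard error = 8 × √(1/20 + 1/10) = 3.10. Noncentrality = 9 / 3.10 = 2.90 on 28 degrees of freedom. Power = 80.1%, so the stated 80% reproduces. The 20 and 10 women randomised are the same 20 and 10 used for power, so there is no allowance for loss.

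**2. When each rule can remove data.**

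- *BMI rule.* Weights fall at months 3, 6, 9 and 12, and entry requires BMI of at least 16.5. Two consecutive values below 16.0 can therefore normally first occur at month 6 (DXA due that day), month 9 (month-6 DXA already due) or month 12 (primary DXA due that day). This rule need not leave a woman without post-baseline BMD.
- *Hospitalisation or serious study-related event.* These can occur at any time. Before month 6 there would be no post-baseline BMD. Between months 6 and 12 there would be a month-6 value only.
- *Overlap.* Some of these women may also be classed as medically unstable, and their assessments then continue.

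**3. Power if women contribute no BMD change** (loss rates assumed; same formula as step 1):

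| Loss | Romosozumab : placebo | Power |
|---|---|---|
| 0% | 20 : 10 | 80.1% |
| 10% | 18 : 9 | 75.4% |
| 20% | 16 : 8 | 70.0% |
| 30% | 14 : 7 | 63.5% |

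**4. Bias of a completer comparison** (all inputs assumed). Suppose the true effect is a constant 9 points and withdrawn women change 5 points less than the others in both arms. Then the completer difference = 9 + (p_romosozumab − p_placebo) × 5, where p is the proportion withdrawn.

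- Equal withdrawal by arm: 9 + 0 = 9.0, no bias.
- 2/20 versus 3/10: 9 + (0.10 − 0.30) × 5 = 8.0.
- 6/20 versus 1/10: 9 + (0.30 − 0.10) × 5 = 10.0.

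The 1.0-point shift is 1.0 / 3.10 = 0.32 of a standard error.

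Now suppose every withdrawn woman has a month-6 DXA showing half the shortfall, and a random-intercept model is fitted (correlation between the 6- and 12-month changes 0.5). The remaining shift is 0.20 × 5 × (1 − 0.5 × 0.5) = 0.75, giving 8.25 or 9.75. If they left before month 6, nothing is recovered. The plan names a random intercept only for Phase 2 Aim 2; using it here is an assumption.

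**5. Would retained scans restore 80% power?** Not necessarily. If 20% stop early and the effect in them is 0 to 4.5 points, the all-randomised effect is 0.8 × 9 + 0.2 × 0 = 7.2 up to 0.8 × 9 + 0.2 × 4.5 = 8.1. Power with all 30 women scanned is then 61.2% to 71.4%.

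**6. Month 24.** Section IV says all women receive the infusion, and the Phase 2 comparison is between sequences that include it. Section VII says that after romosozumab is stopped "BMD returns to approximately baseline levels within 12 months in the absence of follow-up antiresorptive therapy". Including or excluding women who never reach the infusion can therefore give different month-24 estimates. The documents give no month-24 effect or SD, so no size is attached.

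**The case against.** The strongest reply is that the text is silent and forbids nothing. No section says that scans stop, withdrawal terms may appear in consent pages that were not available, and women in hospital may often be classed as medically unstable. This stands: loss of scans is an inference.

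Second, a random effects model fitted to all available DXA by randomised group is compatible with intention-to-treat, and it uses a withdrawn woman's baseline and month-6 values. This also stands. A reader might infer that the drop criteria contradict the intention-to-treat label, and the documents do not support that. What remains is an unstated missing-at-random assumption, and no outcome data at all for women who leave before month 6.

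Third, section I reports a very low drop-out rate in the group's Prolia pilot. It is the only evidence on drop-out in the documents, and it makes the higher assumed losses look pessimistic. It is indirect, because the protocol credits less frequent dosing, whereas this trial injects monthly and these withdrawals are triggered by rule.

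Fourth, the bias figures depend on chosen imbalances between arms, for which the documents give no reason, and the power figures do not justify the remedy (step 5). Both points are right. The case for continued scanning is that it protects the estimate.

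**Conclusion.** The concern holds as a gap in stated data collection that is cheap to close. Three withdrawal criteria operate throughout the primary-endpoint period with no DXA stated afterwards, and the model's missing-data assumption is not given. The exposure is greatest for hospitalisation or a serious study-related event before month 6, and small for the BMI rule.

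Its size cannot be determined. The documents give no withdrawal rate for this trial. A completer comparison is unbiased if withdrawal is equal by arm and the treatment effect is constant. In the assumed imbalances above, the shift is at most 1.0 point, about a third of a standard error. The power figures of 75% and 70% rest on assumed losses of 10% and 20%.

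A reader might go further and infer that the 12-month effect will be biased in a known direction, or that retaining scans secures 80% power. The documents support neither. Nor do they settle which women belong in the month-24 comparison; that choice is the sponsor's.

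**What to change.** Leave the drop criteria and all treatment decisions unchanged.

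1. State that meeting a non-pregnancy drop criterion does not by itself end data collection, extending to the other three criteria what section III already says for medical instability.
2. Ask consenting women to attend the month 6, 12 and 24 DXA visits already in the schedule.
3. Include all available DXA by randomised group in the primary 12-month model, and state its missing-at-random assumption.
4. Report withdrawals by arm, reason, and whether before or after the month-6 DXA.
5. State whether the month-24 comparison includes women who did not receive the infusion.

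A missing-not-at-random sensitivity analysis for values still missing is optional.

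The cost is a short amendment, a consent change if the form describes withdrawal, and retention effort with women who are unwell, some of whom will decline. No procedure is added beyond scans already planned for all 30 women.
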